Rationale for change		Editorial changes and clarifications regarding the conduct of the 6MWT.

## 11.2 GLOBAL AMENDMENT 2

Date of amendment		20 Jul 2018
EudraCT number EU number		2017-004073-14
BI Trial number		1245-0168
BI Investigational Product(s)		Empagliflozin
Title of protocol		A phase III randomised, double-blind trial to evaluate the effect of 12 weeks treatment of once daily EMPagliflozin 10 mg compared with placebo on ExeRcise ability and heart failure symptoms, In patients with chronic HeArt FaiLure with reduced Ejection Fraction ( HFrEF ) (EMPERIAL-reduced)
To be implemented only after approval of the IRB / IEC / Competent Authorities		X
To be implemented immediately in order to eliminate hazard – IRB / IEC / Competent Authority to be notified of change with request for approval		
Can be implemented without IRB / IEC / Competent Authority approval as changes involve logistical or administrative aspects only		
Section to be changed		Abbreviations
Description of change		The following abbreviation was added: AF – Atrial Fibrillation
Rationale for change		The abbreviation was added as the term atrial fibrillation (AF) was included in the protocol.
Section to be changed		Inclusion criteria (Synopsis and Section 3.3.2)
Description of change		Elevated NT-proBNP > 600 pg/ml as analysed at the Central laboratory at Visit 1  Was changed to: Elevated NT-proBNP > 450 pg/ml for patients without atrial fibrillation (AF) OR > 600 pg/ml for patients with AF as analysed at the Central laboratory at Visit 1
Rationale for change		To take into account the influence of atrial fibrillation, the NT-pro BNP threshold has been changed to >450 pg/ml for patients without AF and kept the same at 600 pg/ml for patients with AF. HF guidelines recommend NT-pro BNP >125 pg/ml to assist diagnosis of HFrEF. A higher arbitrary cut-off is selected in clinical trials to increase specificity, as it is followed in this study. Given the essential part of patient selection in this

		trial is EF measurement and performance at 6-minute walk test during screening, the proposed change in NT-pro BNP will not affect the integrity of the trial.
Section to be changed		Flowchart, Section 3.3, Section 6.2.1
Description of change		
The ECG was marked with footnote * in the Flowchart.
 
The following text was added to Flowchart footnote * and Section 6.2.1:
 
The baseline rhythm (e.g. sinus rhythm, AF) of the patient must be clarified (i.e. ECG) and documented at the time the NT-proBNP sample is collected.
 
The following text was added to Section 3.3:
 
If the retest is for the NT-proBNP, the baseline rhythm (e.g. sinus rhythm, AF) of the patient must be clarified (i.e. ECG) and documented at the time the NT-proBNP sample is collected.

Rationale for change		At the time of NT-proBNP measurement, the baseline rhythm of the patient (e.g. sinus rhythm, AF) must be determined (i.e. by ECG) in order to assess, which NT-proBNP cut-off applies for eligibility.

**APPROVAL / SIGNATURE PAGE****Document Number: c17550230****Technical Version Number:3.0****Document Name: clinical-trial-protocol-version-3**

**Title:** A phase III randomised, double-blind trial to evaluate the effect of 12 weeks treatment of once daily EMPagliflozin 10 mg compared with placebo on ExeRcise ability and heart failure symptoms, In patients with chronic HeArt FaiLure with reduced Ejection Fraction (HFrEF) (EMPERIAL - reduced)

## 2. LIST OF ABBREVIATIONS

Term	Definition / description
6MWT	Six-minute walking test
6MWTD	Six-minute walking test distance
ACE	Angiotensin converting enzyme
AE	Adverse Event
AESI	Adverse Event of Special Interest
ALT	Alanine transaminase
ANCOVA	Analysis of covariance
ARB	Angiotensin Receptor Blocker
ARNI	Angiotensin Receptor-Nepilysin Inhibitor
ASA	acetylsalicylic acid
AST	Aspartate transaminase
ATC	Anatomical-Therapeutic-Chemical classification
AUC	Area Under the receiver operating characteristic Curve
BI	Boehringer Ingelheim
BIcMQ	Boehringer Ingelheim customised MedDRA Query
BMI	Body Mass Index
BP	Blood Pressure
bpm	beats per minute
BRPM	Blinded Report Planning Meeting
CEC	Clinical event committee
CHF	Chronic Heart Failure
CHQ	Chronic Heart Failure Questionnaire
CHQ-SAS	Chronic Heart Failure Questionnaire - Self-Administered Standardised format
CKD	Chronic Kidney Disease
CKD-EPI cr	Chronic Kidney Disease Epidemiology Collaboration Equation
CML	Local Clinical Monitor
CTP	Clinical Trial Protocol
CTR	Clinical Trial Report

Term	Definition / description
CRA	Clinical Research Associate
CV	Cardiovascular
DBL	Database lock
DBP	Diastolic Blood Pressure
DKA	Diabetic ketoacidosis
DM	Diabetes Mellitus
DM&SM	Boehringer Ingelheim Data Management And Statistics Manual
ECDF	Empirical cumulative distribution functions
ECG	Electrocardiogramm
eCRF	Electronic Case Report Form
EF	Ejection Fraction
eGFR	Estimated Glomerular Filtration Rate
EMA	European Medicines Agency
EoT	End-of-Text
gCV	Geometric coefficient of variation
HF	Heart Failure
HFrEF	Heart Failure with reduced Ejection Fraction
HHF	Hospitalisation for Heart Failure
HLT	High-Level Term
IC	Informed Consent
ICH	International Conference On Harmonisation
iPD	Important Protocol Deviation
JVD	Jugular Venous Distension
KCCQ	Kansas City Cardiomyopathy Questionnaire
KCCQ-CSS	Kansas City Cardiomyopathy Questionnaire – Clinical Summary Score
KCCQ-TSS	Kansas City Cardiomyopathy Questionnaire - Total Symptom Score
LLT	Lowest Level Term
LVEF	Left Ventricular Ejection Fraction
MedDRA	Medical Dictionary For Regulatory Activities
MMRM	mixed model repeated measure analysis
MRA	Mineralocorticoid receptor antagonist

Term	Definition / description
NT-proBNP	N-Terminal Pro-Brain Natriuretic Peptide
NYHA	New York Heart Association
OC-AD	Observed Case including data After Discontinuation
OC-OT	Observed Case On Treatment
PD	Protocol Deviation
PDMAP	Project Data Management and Analysis Plan
PGI-C	Patient Global Impression of Change
PGI-S	Patient Global Impression of Severity
PRO	Patient Reported Outcome
PT	Preferred Term
pt-yrs	patient years
Q1	Lower Quartile
Q3	Upper Quartile
ROC	Receiver Operating Characteristic
RS	Randomised Set
SAE	Serious Adverse Events
SBP	Systolic Blood Pressure
SCR	Screened Set
SD	Standard Deviation
SE	Standard Error
SEM	Standard Error of Measurement
SensRS	Sensitivity analysis set
SMQ	Standardised MedDRA Query
SOC	System Organ Class
T1DM	Type 1 Diabetes Mellitus
TBILI	Total Bilirubin
TS	Treated Set
TSAP	Trial Statistical Analysis Plan
ULN	Upper Limit of Normal
UTI	Urinary Tract Infections
WCI	Worst Case Imputation

---

Term	Definition / description
WHO DD	World Health Organization Drug Dictionary
Y/N	Yes/No

---

### **3. INTRODUCTION**

*As per ICH E9 (1), the purpose of this document is to provide a more technical and detailed elaboration of the principal features of the analysis described in the protocol, and to include detailed procedures for executing the statistical analysis of the primary and secondary variables and other data.*

*This TSAP assumes familiarity with the Clinical Trial Protocol (CTP), including Protocol Amendments. In particular, the TSAP is based on the planned analysis specification as written in CTP Section 7 “Statistical Methods and Determination of Sample Size”. Therefore, TSAP readers may consult the CTP for more background information on the study, e.g., on study objectives, study design and population, treatments, definition of measurements and variables, planning of sample size, randomisation.”*

*SAS® Version 9.4 will be used for all analyses.*

## **4. CHANGES IN THE PLANNED ANALYSIS OF THE STUDY**

### **4.1 CHANGES NEWLY INTRODUCED FROM THE CLINICAL TRIAL PROTOCOL**

Analyses of the following endpoints have been added:

- Systolic blood pressure
- Diastolic blood pressure
- Body weight

## **5. ENDPOINTS**

### **5.1 PRIMARY ENDPOINT**

The primary endpoint is defined in CTP Section 2.1.2.

### **5.2 SECONDARY ENDPOINTS**

#### **5.2.1 Key secondary endpoints**

The key secondary endpoint is defined in CTP Section 2.1.3. The scoring algorithm for KCCQ-TSS and CHQ-SAS dyspnea can be found in [Appendix 9.4](#).

#### **5.2.2 Secondary endpoints**

Secondary endpoints are listed in CTP Section 2.1.3. The scoring algorithm for the clinical congestion score can be found in [Appendix 9.5](#).

### **5.3 FURTHER ENDPOINTS**

Further endpoints are listed in CTP Section 2.2.2.

Response in KCCQ domains at week 12: Response will be defined as an improvement of at least 5 points.

Response in CHQ domains at week 12: Response will be defined as an improvement of at least 0.5 points. Scoring algorithm for all KCCQ domains and CHQ-SAS domains can be found in [Appendix 9.4](#).

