the early weeks of administration and therefore the peak effect on improving exercise ability is expected to be seen as early as approximately 4-8 weeks from baseline. Thus, a 12 week time point is considered suitable for the assessment of the primary endpoint.

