### 10.3 PATIENT REPORTED OUTCOME

#### 10.3.1 KCCQ (Kansas City Cardiomyopathy Questionnaire)

##### THE KANSAS CITY CARDIOMYOPATHY QUESTIONNAIRE:

The following questions refer to your **heart failure** and how it may affect your life. Please read and complete the following questions. There are no right or wrong answers. Please mark the answer that best applies to you.

1. **Heart failure** affects different people in different ways. Some feel shortness of breath while others feel fatigue. Please indicate how much you are limited by **heart failure** (shortness of breath or fatigue) in your ability to do the following activities over the past 2 weeks.

Place an **X** in one box on each line

Activity	Extremely Limited	Quite a bit Limited	Moderately Limited	Slightly Limited	Not at all Limited	Limited for other reasons or did not do the activity
Dressing yourself						
Showering/Bathing						
Walking 1 block on level ground						
Doing yardwork, housework or carrying groceries						
Climbing a flight of stairs without stopping						
Hurrying or jogging (as if to catch a bus)						

2. Compared with 2 weeks ago, have your symptoms of **heart failure** (shortness of breath, fatigue or ankle swelling) changed? My symptoms of **heart failure** have become . . .

Much worse      Slightly worse      Not changed      Slightly better      Much better      I've had no symptoms over the last 2 weeks

3. Over the past 2 weeks, how many times did you have **swelling** in your feet, ankles or legs when you woke up in the morning?

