### 7.6.1 Binary endpoints

For the following binary endpoints descriptive analyses will be complemented by an exploratory chi-square test to compare response between treatment groups.

- Increase in 6MWT  $\geq 30$  m from baseline at week 12
- Response in KCCQ domains at week 12, as defined in [Section 5.3](#). A forest plot of response at week 12 for each domain by treatment will be shown.
- Response in CHQ domains at week 12, as defined in [Section 5.3](#). A forest plot of response at week 12 for each domain by treatment will be shown.

Descriptive statistics are planned for all other binary endpoints:

- Occurrence of HHF and Cardiovascular (CV) death
- Occurrence of all-cause mortality
- Occurrence of CV death
- Occurrence of all-cause hospitalisation (first and recurrent)
- Occurrence of hospitalisation for HF (first and recurrent)
- Occurrence of all-cause emergency room visits (first and recurrent)
- Emergency room visit for HF (requires use of i.v. diuretics; first and recurrent)
- Occurrence of unscheduled outpatient visit (first and recurrent)
- Intensification of diuretic therapy (adding a new diuretic, increase of dose)
- Occurrence of MI (fatal or non-fatal)
- Occurrence of Stroke (fatal or non-fatal)
- Occurrence of TIA

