### 9.4.1 Kansas City Cardiomyopathy Questionnaire (KCCQ)

There are 10 summary scores within the KCCQ, which are calculated as follows:

1. Physical Limitation

Code responses to each of Questions 1a-f as follows:

- Extremely limited = 1

- Quite a bit limited = 2
- Moderately limited = 3
- Slightly limited = 4
- Not at all limited = 5
- Limited for other reasons or did not do = <missing value>

If at least three of Questions 1a-f are not missing, then the Physical Limitation Score is calculated as follows:

$$\text{Physical Limitation Score} = 100 * [(\text{mean of Questions 1a-f actually answered}) - 1] / 4$$

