## 2. Symptom Stability

Code the response to Question 2 as follows:

- Much worse = 1
- Slightly worse = 2
- Not changed = 3
- Slightly better = 4
- Much better = 5
- I've had no symptoms over the last 2 weeks = 3

If Question 2 is not missing, then the Symptom Stability Score is calculated as follows:

$$\text{Symptom Stability Score} = 100 * [( \text{Question 2} ) - 1] / 4$$

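### The 5-point KCCQ response rule takes in Symptom Stability, which already rates change over two weeks, so its responder result is not improvement since baseline (low impact)

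*SAP*

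**What the plan says.** The rule in SAP 5.3 reads "Response in KCCQ domains at week 12: Response will be defined as an improvement of at least 5 points". The same section adds "Scoring algorithm for all KCCQ domains and CHQ-SAS domains can be found in" Appendix 9.4.

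SAP Appendix 9.4.1 opens with "There are 10 summary scores within the KCCQ, which are calculated as follows", and Symptom Stability is the second of the ten. It rests on Question 2 alone: "If Question 2 is not missing, then the Symptom Stability Score is calculated as follows", namely 100 × (Question 2 − 1)/4. Answers are coded 1 (much worse) to 5 (much better), with 3 for no change. The sixth option gets the middle code too: "I've had no symptoms over the last 2 weeks = 3".

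The question is printed in Protocol Appendix 10.3.1. It begins "Compared with 2 weeks ago, have your symptoms of" heart failure, and asks the patient to say whether they changed.

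SAP 7.6.1 compares domain response between arms with an exploratory chi-square test and adds: "A forest plot of response at week 12 for each domain by treatment will be shown". SAP 7.6.3 covers change from baseline in the individual KCCQ domains at weeks 6 and 12. It plans an MMRM with visit-by-treatment and baseline-by-visit terms, plus descriptive statistics for both the visit value and the change. None of these sections excludes Symptom Stability or gives it a response definition of its own.

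**The concern.** The other KCCQ domains in SAP Appendix 9.4.1 score a patient's state, so week 12 minus baseline is the change over the trial. Symptom Stability scores a change already. Its week-12 value describes roughly the two weeks before that visit, and its baseline value describes the two weeks before randomisation. The difference shows whether the recent trend is better than the earlier trend. It does not show whether symptoms are better than at baseline.

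The rule therefore misclassifies in both directions. A gain made in mid-treatment and then held is invisible if the baseline answer was no change or better. A return from worsening to steady counts as a response. The result would stand in the same forest plot as domains for which the rule does measure improvement since baseline. A reader could take a null row as absence of lasting symptom benefit.

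**Working it through.** The plan states no power, sample size or error rate for this endpoint, so there is no figure to reproduce. The check scores every possible answer and applies the rule to every baseline/week-12 pair.

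**Inputs.** Codes and formula from SAP Appendix 9.4.1; the cut-off of 5 from SAP 5.3.

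**Scores.** With 100 × (code − 1)/4:
- much worse: 100 × 0/4 = 0
- slightly worse: 100 × 1/4 = 25
- not changed: 100 × 2/4 = 50
- no symptoms (code 3): 50
- slightly better: 100 × 3/4 = 75
- much better: 100 × 4/4 = 100

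**Change, week 12 minus baseline** (R = responder at 5 points or more):

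| Baseline score | Week 12: 0 | 25 | 50 | 75 | 100 |
|---|---|---|---|---|---|
| 0 | 0 | +25 R | +50 R | +75 R | +100 R |
| 25 | −25 | 0 | +25 R | +50 R | +75 R |
| 50 | −50 | −25 | 0 | +25 R | +50 R |
| 75 | −75 | −50 | −25 | 0 | +25 R |
| 100 | −100 | −75 | −50 | −25 | 0 |

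**Reading the table.**
- Not changed at baseline, improved in mid-treatment, steady since: 50 − 50 = 0, non-responder.
- Not changed at baseline, symptom-free at week 12: 50 − 50 = 0, non-responder.
- Slightly better at baseline, then a held gain or no symptoms: 50 − 75 = −25, non-responder.
- Slightly worse at baseline, not changed at week 12: 50 − 25 = +25, responder with no improvement reported on either occasion.
- Much worse or slightly worse at baseline, then a held gain: +50 or +25, responder.
- Not changed at baseline and still improving before week 12: +25 or +50, responder.

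**Does another cut-off help?** Count the six answers separately at each visit, which gives 36 pairs. In the order much worse, slightly worse, not changed, no symptoms, slightly better, much better at baseline, the responder pairs number 5 + 4 + 2 + 2 + 1 + 0 = 14. The smallest non-zero change is 25, so every cut-off above 0 and up to 25 gives the same 14. At 26 points, 8 remain. A change of 0 is a non-response at any cut-off above 0, so the steady improver with a baseline score of 50 is never recovered. These are counts of possible pairs, not expected proportions of patients.

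**Is the MMRM in SAP 7.6.3 affected?** Write Y for the score at visit v, B for baseline and T for treatment. The model is Y − B = a(v) + t(v)·T + b(v)·B + error. Moving B to the right gives Y = a(v) + t(v)·T + [b(v) + 1]·B + error. The treatment contrasts t(v) are identical, so at weeks 6 and 12 they already compare the score itself between arms.

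**The case against.** **Symptom Stability is not named in SAP 5.3, 7.6.1 or 7.6.3.** Its inclusion is inferred. The ten scores in Appendix 9.4.1 include composites, while Protocol 2.2.2 lists the overall and clinical summary scores apart from the individual domains. The appendix list is therefore not itself the list of analysed domains. This stands as a caution. But Symptom Stability is not a composite, the text speaks of all and of each domain, and nothing takes it out. A programmer following the plan would include it.

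**A reader might infer that every lasting improver is lost, or that the score carries no information.** Neither holds. Patients who were worsening at baseline and then hold a gain are counted. So are patients who rise to a higher category because they are still improving near week 12, from a baseline of 75 or less. The score is a limited measure of recent trend.

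**A reader might infer that the sponsor expects symptoms to have levelled off before week 10.** Protocol 3.2 writes of the peak effect on exercise "ability is expected to be seen as early as approximately 4-8 weeks from baseline". That concerns walking, and it gives an early bound. No plateau time for symptoms is stated. Protocol 3.3.2 does require clinical stability at randomisation, which makes a baseline answer of no change plausible. That is the investigator's judgement, though, not the patient's answer to Question 2.

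**The consequences are small.** This stands. The test is exploratory and outside the testing hierarchy. Randomisation gives no reason for the classification to favour either arm if treatment has no effect. Symptom frequency, symptom burden and the Total Symptom Score are scored separately from other questions.

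**Conclusion.** The responder rule is wrong as written for this one domain, with low impact. It classes as non-responders those patients who answer no change or better at baseline, improve, and then hold the gain or become symptom-free. It classes as responders some patients who report no improvement. The scoring arithmetic is exact. The number of patients concerned is unknown, because no distribution of Question 2 answers is given.

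The conclusion rests on reading the domain wording in SAP 5.3 and 7.6.1 at face value. It does not reach the key secondary endpoint: SAP Appendix 9.4.1 builds the Total Symptom Score from Questions 3 to 9, and neither the Clinical nor the Overall Summary Score uses Question 2. It does not reach the MMRM treatment contrasts in SAP 7.6.3, where only the descriptive change values are hard to interpret. Nor is it a complaint about the figure 5, since raising or lowering the threshold would not cure it. The other domains and all confirmatory analyses are unaffected.

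**What to change.** - **SAP 5.3:** name the KCCQ domains that the response definition covers, and exclude Symptom Stability.
- **SAP 7.6.1:** drop Symptom Stability from the chi-square test and from the forest plot.
- **SAP 7.6.3:** for Symptom Stability, replace the descriptive change from baseline with the visit value at weeks 6 and 12 by arm, as the proportions below, at and above 50. A footnote should say that 50 covers both no change and no symptoms. The MMRM can stay as it is.

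The cost is a short edit in three SAP sections, one row less in the forest plot and one small replacement table. No new data are needed.

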### **5.4 OTHER VARIABLES**

#### **5.4.1 Demographic and other baseline characteristics**

Blood pressure: Baseline SBP and DBP are taken from the vital signs assessment. If no vital signs assessment is available, the value before the start of the 6MWT will be used.

Region will be defined according to [Table 9.1:1](#)

Heart rate will display values entered in the electronic case report form (eCRF) as ‘pulse’.

#### **5.4.2 Treatment compliance**

Overall compliance (%) to study medication will be calculated as a weighted average of reported compliance. Weights will be determined based on actual visit dates. Compliance will be displayed for the treated set.

### **5.4.3 Treatment exposure**

Duration of exposure will be calculated as day of last intake of study drug – day of first intake of study drug + 1 day.

## 6. GENERAL ANALYSIS DEFINITIONS

### 6.1 TREATMENTS

There will be 3 study intervals in this trial: screening, study treatment phase (with either empagliflozin 10mg or matching placebo) and follow-up. The purpose of the definitions below is to describe the different study intervals.

Table 6.1: 1 Treatment regimens / study intervals

Label in database	Label in tables and listings	Interval	Start date
SCREENING	Screening	Screening	Date of informed consent
PLACEBO/ BI 10773 10 MG	Placebo/Empa 10 mg	Treatment	Date of first administration of double-blind study treatment
FOLLOW-UP	Post Pbo/Post Empa	Follow up	Date of last administration of study drug + 1 day

Details on the definition of the treatment period for different endpoints are listed in [Table 6.1:2](#). The efficacy analyses will follow the intention-to-treat (ITT) principle. For the assignment of patients to treatment groups this means that patients will be analysed as randomised.

For safety analyses, patients will be also assigned to the treatment groups as randomised.

If a patient erroneously receives the wrong trial drug, all future medication packs will be dispensed as scheduled for the treatment group to which the patient was randomised. Therefore, the adverse events will be analysed as per randomised treatment, which is expected to reflect the prevailing treatment. In exceptional cases that a patient took the wrong treatment, all adverse events that occur while being on the wrong treatment will be listed and analyses of this data are described in [section 7.8.1.6](#).

Table 6.1: 2 Endpoint-specific assignment to the on-treatment phase

Endpoint	Last day of assignment to on-treatment phase (days after last intake of study medication)
6MWT distance	1
PRO endpoints (key secondary endpoints)	7
Adverse events	7
Safety laboratory measurements	3
Heart rate	1
Body weight	1
Creatinine and estimated glomerular filtration rate (eGFR)	1
Blood pressure	1

